#### **Sample Processing for L-Ascorbic Acid Analysis**

Plasma and WBC preparation at KGK Canadian Clinic (██████████):

1. Whole blood will be collected in two 8 mL sodium-heparin CPT™ vacutainer tube for plasma and WBC L-ascorbic acid analysis.
2. After the vacutainer tube is completely filled the tube will be inverted 8-10 times to ensure a complete mixing of blood and anticoagulant.
3. Sodium-heparin CPT™ vacutainer tubes will be immediately centrifuged for 20 minutes at 1500 RCF at 18 – 25 °C
4. 2 mL of plasma will be aliquoted into two amber cryovials and frozen at -80°C
5. The cell layer (whitish layer under the plasma layer) will be collected with a Pasteur pipette and transferred to a conical centrifuge tube that is in an ice slurry
6. PBS (without Ca++ or Mg++) will be added to the conical tube to bring the volume to 15 mL
7. The conical tube will be capped and inverted 5 times to mix the cells
8. The conical tube will be centrifuged for 15 minutes at 300 CRF at 4°C
9. The supernatant will be aspirated as much as possible without disturbing the cell pellet
10. The cell pellet will be resuspended by gently vortexing the conical tube
11. PBS (without Ca++ or Mg++) will be added to the conical tube to bring the volume to 10 mL
12. The conical tube will be capped and inverted 5 times to mix the cells
13. The conical tube will be centrifuged for 10 minutes at 300 CRF at 4°C
14. The supernatant will be aspirated as much as possible without disturbing the cell pellet
15. The cell pellet (WBC mononuclear cells) will be suspended in PBS (without Ca++ or Mg++) and transferred to amber cryovial and frozen at -80°C
16. One cryovial containing plasma will be delivered to LifeLabs for analysis and the second plasma cryovial will be retained at KGK
17. One cryovial containing WBC will be delivered to Mount Sinai Laboratory for analysis and the second WBC cryovial will be retained at KGK
18. Throughout this process the sample will be protected from light.

Urine Processing at KGK Canadian Clinic ( [REDACTED] ):

1. Total urine will be collected at pre-dose (0 h) and at post-dose (0-4h, 4-8h and 8-24h).
2. Total volume will be recorded for each collection period.
3. Urine collected pre and post-dose will be kept at 4°C until the end of each collection period.
4. At the end of each collection period urine will be agitated to ensure homogeneity of the collected urine sample and 8 mL sample will be transferred into a opaque tube.
5. The opaque tube will be centrifuged at 1000 x g for 20 minutes at 4°C.
6. 2 mL aliquot of the supernatant will be transferred into two amber cryovials and stored at -80°C.
7. One cryovial will be delivered to Mount Sinai Laboratory for analysis and one vials will be retained at KGK.
8. Throughout this process the sample will be protected from light.

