# 6 STUDY ASSESSMENTS

See Appendix 1 for the schedule of assessments and procedures, and Appendix 1a for time points for blood and urine sampling:

- Table 1A: A total of twelve (12) time points for blood sampling including baseline prior to dosing at 0h, and 0.5, 1, 2, 3, 4, 5, 6, 8, 10, 12 and 24 h post dosing for ascorbic acid analysis.
- Table 1B: A total of four time points for blood safety parameters.
- Table 1C: A total of six time points for urine ascorbic acid.

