#### Urine Collection:

At screening (Visit 1), a urine pregnancy test will be done at the KGK Synergize clinic on females of childbearing potential.

At Baseline (Visit 2), urine will be collected for L-ascorbic acid analysis prior to dosing and total volume recorded. A sample will be retained for L-ascorbic acid analysis. Urine will be collected during the following post-dose time intervals 0-2h, 2-4h, 4-8h, and 8-12h and the total volume of each post-dose time interval will be recorded. A sample will be retained from each post-dose time interval for L-ascorbic acid analysis.

At visit 3, urine will be collected from 12-24h (a collection container will be dispensed to participants and they will be instructed to collect their urine up until their 24h post-dose appointment) and total volume will be recorded. A sample will be retained for L-ascorbic acid analysis.

At visit 4, urine will be collected for L-ascorbic analysis prior to dosing and total volume recorded. A sample will be retained for L-ascorbic acid analysis. Urine will be collected during the following post-dose time intervals 0-2h, 2-4h, 4-8h, and 8-12h and total volume of each post-dose time interval will be recorded. A sample will be retained from each post-dose time interval for L-ascorbic acid analysis.

At visit 5, Urine will be collected from 12-24h (a collection container will be dispensed to participants and they will be instructed collect their urine up until their 24h post-dose appointment) and the total volume will be recorded. A sample will be retained for L-ascorbic acid analysis.

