### Schedule of Assessments

Procedures/assessments	Visit 1 Screening		Visit 2 Baseline 0-12 hour	Visit 3 24 hour		Visit 4 0-12 hour	Visit 5 24 hour End of study
	1 st study period		1 st study period	1 st study period		2 nd study period	2 nd study period
Informed Consent	X						
Review of Inclusion/Exclusion criteria	X		X				
Review of medical history/current health status	X		X			X	
Review of concomitant therapies	X		X	X		X	X
Review adverse events				X		X	X
Height*, weight, blood pressure and heart rate	X		X	X		X	X
Randomization			X				
Physical Exam			X				
Nutrition counselling	X						
Laboratory Tests				X			
Blood sample collection for CBC, electrolytes, HbA1c*, creatinine, eGFR, AST, ALT, and bilirubin analysis	X					X	X
Urine pregnancy test	X						
Blood samples: Pre-dose (t=0) and Post-dose (30 min, 1h, 2h, 3h, 4h, 5h, 6h, 8h, 10 h, 12 h) for L-Ascorbic Acid analysis			X			X	
Blood samples: 24 hours for L-Ascorbic Acid analysis				X			X
Pre-dose Urine sample for L-Ascorbic Acid analysis			X			X	
Post-dose urine samples: 0-2h, 2-4h, 4-8h, 8-12h post-dose L-Ascorbic Acid analysis			X			X	
Dispense urine collection kits for 8-24h urine collection: L-ascorbic acid			X			X	
Return post-dose urine sample collection: 12-24h post-dose L-Ascorbic Acid analysis				X			X
IP or Comparator Dispensed			X			X	
Breakfast, lunch, and dinner provided			X			X	
Study diary dispensed			X	X		X	
Study diary returned				X		X	X
24h-food record dispensed			X			X	
24h-food record returned				X			X
7-day food record dispensed	X			X			
7-day food record returned				X			

\* Will only be measured at screening visit (Visit 1)

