## 13.2 Appendix 1a Time Points for Sampling

Blood Draw for Ascorbic Acid Measurement (Table 1A), Safety Parameters (Table 1B) and Urine Collection (Table 1C). One of two vials will be retained.

Table 1A. Time Points for Blood Draw – Ascorbic Acid Measurement Blue cells are vials that will be aliquoted from tubes in green cells													
		Visits 2 & 4										Visits 3 & 5	
Timing (Hour)		0 h	30 min	1 h	2 h	3 h	4 h	5 h	6 h	8 h	10 h	12 h	24 h
Number of Vacutainer tubes (8 mL/tube)		2	2	2	2	2	2	2	2	2	2	2	2
Total blood volume (mL)		16	16	16	16	16	16	16	16	16	16	16	16
Number of vials for Plasma		2	2	2	2	2	2	2	2	2	2	2	2
Number of cryovials for WBC		2	2	2	2	2	2	2	2	2	2	2	2

Table 1B. Time Points for Blood Draw – Safety Parameters					
Timing		Screening Visit 1		Visit 4 0 h	Visits 3 & 5 24 h
Number of vacutainer tubes		2 tubes (4mL/tube) 1 tube (5mL/tube)		1 tube (4mL/tube) 1 tube (5mL/tube)	1 tube (4mL/tube) 1 tube (5mL/tube)
Total volume (mL)		13 mL		9 mL	9 mL

Table 1C. Time Points for Urine Collection – Ascorbic Acid Measurement														
	Visits 2 & 4											Visits 3 & 5		
Hour	0 h	1 h	2 h	3 h	4 h	5 h	6 h	7 h	8 h	9 h	10 h	11 h	12 h	12 h → 24 h
Timing	Prior to Dosing	0-2 h Post-dose		2-4 h Post-dose		4-8 h Post-dose			8-12 h Post-dose			13-24 h post-dose		
Number of vials	2 Vials	2 Vials		2 Vials		2 Vials			2 Vials			2 Vials		

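### Step 1 of Urine Processing (Section 6.9) sets three post-dose urine periods where the rest of the plan sets five; following it would merge planned intervals, with minor impact

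*Combined protocol and SAP*

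**What the plan says.** The bench procedure for urine (Section 6.9, Sample Processing for L-Ascorbic Acid Analysis, Urine Processing) opens with "Total urine will be collected at pre-dose (0 h) and at post-dose (0-4h, 4-8h and 8-24h". The steps after it record one volume per collection period and, when the period ends, mix the urine and draw a single 8 mL portion. That portion is centrifuged and split into two vials, one for assay and one retained.

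A few paragraphs earlier, the Urine Collection text of the same section sets finer intervals for the clinic day: "Urine will be collected during the following post-dose time intervals 0-2h, 2-4h, 4-8h, and 8-12h and the total volume of each post-dose time interval" is to be recorded. It adds "A sample will be retained from each post-dose time interval for L-ascorbic acid analysis". For the home part it says "At visit 3, urine will be collected from 12-24h (a collection container will be dispensed to participants". Visits 4 and 5 repeat the same pattern. Sections 6.3, 6.4, 6.6 and 6.7 agree with this, as do the sample and return rows of the Appendix 1 schedule. Section 6 gives the count: "Table 1C: A total of six time points for urine ascorbic acid".

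Two labels elsewhere do not match. The dispensing row of Appendix 1 reads "Dispense urine collection kits for 8-24h urine collection: L-ascorbic acid", and the timing row of Table 1C in Appendix 1a gives the last interval as "13-24 h post-dose".

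Urine results are to be reported in µM at each time point (Section 6.9, Analytical method) and drawn as individual and mean line graphs over 24 h (Section 8.3). Section 8.3 also states that the white-cell and urine data serve information only.

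**The concern.** Step 1 is an operative instruction, not background. It defines the collection periods on which every later urine step depends: the volume, the mixing and the aliquot. A technician working from that list would combine urine that the visit sections want kept apart. Once two intervals have been mixed and sampled once, their separate concentrations are gone. The retained vial does not help, because it comes from the same mixed urine. At stake is the shape of the urine profile over 24 h for each product, which the plan intends to report and plot.

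**Working it through.** **Inputs**

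| Source | Post-dose intervals (h) | Pre-dose |
|---|---|---|
| Sections 6.3, 6.4, 6.6, 6.7; Section 6.9 Urine Collection; Appendix 1 sample and return rows | 0-2, 2-4, 4-8, 8-12, 12-24 | yes |
| Section 6.9 Urine Processing, step 1 | 0-4, 4-8, 8-24 | yes |
| Section 6, stated count | six time points in all | – |

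**1. Reproduce the plan's own figure.** Visit scheme: 1 pre-dose + 5 intervals = 6. This matches the count of six in Section 6. Step 1: 1 + 3 = 4. This does not match.

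**2. Map one scheme onto the other.**
- 0-4 h = 0-2 h + 2-4 h: two intervals become one.
- 4-8 h = 4-8 h: unchanged.
- 8-24 h = 8-12 h (4 h in clinic) + 12-24 h (12 h at home): two intervals become one.

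Four of the five planned post-dose intervals lose their own sample. Only 4-8 h survives.

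**3. Number of samples.** With two periods and 30 completers:
- Visit scheme: 6 × 2 × 30 = 360.
- Step 1: 4 × 2 × 30 = 240.
- Difference if step 1 were followed throughout: 120 samples.

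**4. Why the split cannot be recovered.** Let two adjacent intervals have volumes V1, V2 and concentrations C1, C2. The mixed sample gives

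C = (V1·C1 + V2·C2) / (V1 + V2),

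and only the sum V1 + V2 is recorded. One measured concentration cannot determine both C1 and C2. The reverse always works: from the finer intervals, the coarser values can be calculated with this formula.

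**5. What is not lost.** Hours covered under the visit scheme: 2 + 2 + 4 + 4 + 12 = 24. Under step 1: 4 + 4 + 16 = 24. Each scheme is contiguous and has no internal overlap. Because (V1 + V2)·C = V1·C1 + V2·C2, total excretion over 0-24 h could be calculated under either.

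**The case against.** The strongest reply is that the plan is clear apart from one line. The same six collections appear in the visit sections, the Urine Collection text, most of the schedule and the stated count. The readable parts of the Appendix 6 flow chart also use 2-4, 4-8, 8-12 and 12-24 h. Urine is informational, is not named in the outcomes list of Section 2, has no hypothesis test, and does not enter the Cmax analysis. At worst, a descriptive graph would have four points instead of six.

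Most of this stands and sets the size of the point. It does not remove the conflict, because step 1 heads the list that laboratory staff would follow. The flow chart is not a safe fallback either: the readable 2-4 h and 4-8 h charts tell staff to label post-dose vials as pre-dose.

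A reader might infer more than the documents support:

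- **Total 0-24 h excretion would be double-counted or incomplete.** Each scheme covers 24 h without overlap, and no analysis of cumulative excretion is specified.
- **The kit row shows a real overlap of 4 of 16 h (25%).** Participants stay in clinic until the 12 h blood draw. Sections 6.3 and 6.6 describe the containers as being for 12-24 h, and the return row of the same schedule says 12-24 h. The row is mislabelled; no overlapping collection is shown.
- **Table 1C leaves 1 of 12 h (8%) uncollected.** The hour heading of that same column runs from 12 h to 24 h, and the Urine Collection text starts at 12 h. Nothing tells anyone to discard the urine of the first hour.
- **The error could differ between products.** This is a single-site cross-over, the visit instructions are the same in both periods, and each participant is to receive both products. No route to such a difference is shown.
- **Section 6.9 as a whole is wrong.** Its Urine Collection text sets out all the planned intervals. The fault is in one processing step.

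**Conclusion.** The contradiction is real and the size is minor. If step 1 were followed, each test period would yield four urine samples instead of six. The intervals 0-2 and 2-4 h, and 8-12 and 12-24 h, would be merged irreversibly, so the urine concentrations by time point and the line graphs could not be produced as specified. Full 0-24 h coverage and the primary plasma Cmax analysis would be untouched.

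This rests on two assumptions. The first is that staff would take the periods in step 1 literally when they record volumes and draw aliquots. The second is that the six-collection scheme is the intended one; its repetition across the plan and its agreement with the stated count support that. The documents do not show which instruction staff would follow in practice, so the loss is conditional. This is an internal inconsistency in wording, not a flaw in the design.

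**What to change.** Change step 1 of Urine Processing to list pre-dose, 0-2, 2-4, 4-8, 8-12 and 12-24 h. Correct the two stray labels to match: the kit-dispensing row of Appendix 1 from 8-24 h to 12-24 h, and the last timing entry of Table 1C from 13-24 h to 12-24 h. Do this before the first dosing visit, since merged urine cannot be separated later.

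The cost is three wording corrections, handled as an amendment if the protocol is already approved. No sample, visit or assay is added beyond the six collections per period that the plan already counts.

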### **Analytical method for L-Ascorbic acid level**

Plasma samples will be frozen and protected from light prior to being delivered to LifeLabs (████████) for analysis of L-ascorbic acid by standard procedures using HPLC methodology. Sample will be processed as follows:

1. Sulfosalicylic acid will be added to the sample to precipitate proteins and to extract ascorbic acid.
2. The supernatant will then be separated and quantified by HPLC using a reverse phase column and electrochemical detector.

WBC and Urine samples will be frozen and protected from light prior to being delivered to Mount Sinai laboratory (████████) for analysis of L-ascorbic acid by ELISA method. Sample will be processed at Mount Sinai Laboratory as follows:

1. 50 µl of Standard will be added to each Standard well, 50 µl of Sample will be added to each Sample well, and 50 µl of Sample Diluent will be added to each Blank/Control well. All Standards, samples and Sample Diluent are analyzed in duplicate.
2. 100 µl of HRP-conjugate reagent will be added to each well, and covered with a Closure Plate Membrane and incubate for 60 minutes at 37°C.
3. The plate will be washed 4 times.
4. To each well 50 µl of Chromogen Solution A will be added and 50 µl Chromogen Solution B will be added successively.
5. The plate will be protected from light and incubated for 15 min at 37°C.
6. After incubation 50 µl of Stop Solution will be added to each well.
7. Optical Density (O.D.) will be read at 450 nm using an ELISA reader within 15 minutes after adding Stop Solution (5 minutes is the optimal reading time).

All measured vitamin C concentrations in µM will be used in report for plasma, WBC and urine samples at each time point during the study.

### **6.10 Termination of the Trial**

In the case of premature termination of the trial, participating investigators/participants, and the Institutional Review Board must be promptly informed of the termination.

### **6.11 Protocol Amendments**

If amendments to the study protocol are required after approval such changes will be captured in writing the reasons for the change documented and signed and dated by the sponsor. Any such amendments may be subject to IRB and Health Canada review/approval prior to implementation. Exception: if it becomes necessary to alter the protocol to eliminate an immediate hazard to participants, an amendment may be implemented prior to IRB approval.

In this circumstance, the Investigator must notify IRB and Health Canada in writing within five (5) working days of the implementation.

## **7 Safety Instructions and Guidance**

### **7.1 Adverse Events and Laboratory Abnormalities**

#### **7.1.1 Adverse Events**

An adverse event (AE) is any untoward medical occurrence in a clinical investigation participant who has been administered an investigational product and which does not necessarily have a causal relationship with the investigational product. An AE can be any unfavorable and unintended sign (including an abnormal laboratory finding), symptom, or disease temporally associated with the use of a product, whether or not it is considered related to that product. Pre-existing conditions which worsen during a study are to be reported as AEs.

During the study, participants should record any adverse effects in their diary. At each visit the participant will be asked "Have you experienced any difficulties or problems since I saw you last"? Any adverse events (AEs) will be documented and in the study record and will be classified according to the description, duration, intensity, frequency, and outcome. The Qualified Investigator will assess any AEs and decide causality.

Intensity of AEs will be graded on a three-point scale (mild, moderate, severe) and reported in detail in the study record.

Mild:	Awareness of event but easily tolerated
Moderate:	Discomfort enough to cause some interference with usual activity
Severe:	Inability to carry out usual activity

The causality relationship of investigational product to the adverse event will be assessed by the Qualified Investigator as either:

Most probable:	There is a reasonable relationship between the investigational product and AEs. The event responds to withdrawal of investigational product (dechallenge) and recurs with rechallenge when clinically feasible.
Probable:	There is a reasonable relationship between the investigational product and AEs. The event responds to dechallenge.
Possible:	There is a reasonable relationship between the investigational product and AEs. Dechallenge information is lacking or unclear.

Unlikely:	There is a temporal relationship to the investigational product administration but there is no reasonable causal relationship between the investigational product and the AEs.
Not related:	No temporal relationship to the investigational product administration or there is a reasonable causal relationship between non-investigational product, concurrent disease or circumstance and the AEs.

#### **7.1.2 Serious Adverse Event**

A serious adverse event (SAE) is any experience that suggests a significant hazard, contraindication, side effect or precaution. It is any AE that results in any of the following outcomes:

- Death
- A life-threatening adverse event
- Inpatient hospitalization or prolongation of existing hospitalization
- A persistent or significant disability or incapacity
- A congenital anomaly/birth defect in the offspring of a participant who received the study product
- Important medical events that may not be immediately life-threatening or result in death or hospitalization but may jeopardize the participant or may require intervention to prevent one of the outcomes listed above. Examples of such events are intensive treatment in an emergency room or at home for allergic bronchospasm; blood dyscrasias or convulsions that do not result in hospitalization; or the development of drug dependency or drug abuse.

#### **7.1.3 Unexpected Adverse Reaction**

An unexpected adverse reaction is an adverse reaction, the nature and severity of which is not consistent with the applicable product information (e.g., Investigator's Brochure for an unapproved investigational product or package insert/summary of product characteristics for an approved product).

#### **7.1.4 Laboratory Test Abnormalities**

The investigator must assess the clinical significance of all abnormal laboratory values as defined by the compendium of normal values for the reference laboratory.

Any investigational product emergent abnormal laboratory result which is clinically significant, i.e., meeting one or more of the following conditions, should be recorded as a single diagnosis on the AEs form in the study record:

- Accompanied by clinical symptoms

- Leading to interruption or discontinuation of the investigational product
- Requiring a change in concomitant therapy

This applies to any protocol and non-protocol specified laboratory result from tests performed after the first dose of the investigational product, which falls outside the laboratory reference range and meets the clinical significance criteria for liver and kidney tests as well as for hematology and clinical chemistry, etc. This does not apply to any abnormal laboratory result which falls outside the laboratory reference range but which does not meet the clinical significance criteria or those which are a result of an AE which has already been reported.

Any laboratory result abnormality fulfilling the criteria for a serious adverse event (SAE) should be reported as such, in addition to being reported as an AE in the study record.

## **7.2 Treatment and Follow-up of AEs and Laboratory Abnormalities**

### **7.2.1 Treatment and Follow-up of AEs**

AEs, especially those for which the relationship to the investigational product is suspected, should be followed up until they have returned to baseline status or stabilized. If after follow-up, return to baseline status or stabilization cannot be established, an explanation should be recorded in the study record.

### **7.2.2 Treatment and Follow-up of Laboratory Abnormalities**

In the event of participant-initiated withdrawal or clinically significant unexplained abnormal laboratory test values, the participant will be withdrawn from receiving study product. Following this, the participant will be encouraged to have a termination visit where blood will be withdrawn for safety and any other relevant information.

